#### 7.1.2 Missing Data

There will be no imputation of incomplete or missing data.

Plasma concentrations that are below the limit of quantification (BLQ) will be treated as zero in the summarizing concentration values and deriving of PK parameters. These values will be flagged in the data listings.

### 7.2 Analysis Sets

The following analysis sets will be used for analysis and presentation of the study data:

- Safety Set: The safety set will consist of all subjects who are enrolled and received at least 1 dose of study drug. Subjects in this analysis set will be used for demographic, baseline characteristics, and safety summaries.

- PK Set: The PK set will consist of all subjects who are enrolled, receive at least 1 dose of trial drug, and have at least 1 measurable plasma TAK-906 concentration.

All subjects in the PK set with valid PK parameter estimates will be included in the summaries and analyses for that parameter. Decisions regarding inclusion or exclusion of data from PK analysis for subjects who are noncompliant with the dosing schedule, or who have incomplete data, will be made on a case-by-case basis, but the data will be presented in data listings regardless.

### 7.3 Disposition of Subjects

Study Information, including date of first subject signing Informed Consent Form (ICF), date of first/last study drug, date of last subject's last visit/contact, date of last subject's last procedure for collection of data for primary endpoint, Medical Dictionary for Drug Regulatory Activities (MedDRA) Version, World Health Organization Drug Dictionary (WHODrug) Version, and SAS Version, will be tabulated.

The eligibility of subjects will be summarized, along with the primary reasons of screen failure as recorded in eCRF.

The number and percentage of subjects who comprised each analysis set will be summarized.

Disposition of all enrolled subjects will be tabulated. Categories will include:

- Subjects who were enrolled but not dosed.
- Subjects who completed the study.
- Subjects who prematurely discontinued study.
- Primary reasons for discontinuing study, as entered on the eCRF.

### 7.4 Demographic and Other Baseline Characteristics

Demographic and study baseline characteristics, including age at informed consent, gender, ethnicity, race, height (cm), weight (kg), and body mass index ( $\text{kg}/\text{m}^2$ ), will be summarized.

There will be no inferential analysis of demographic and baseline characteristics.

### 7.5 Medical History and Concurrent Medical Conditions

Medical history is defined as significant conditions or diseases that resolved at or prior to the time of informed consent. Concurrent medical conditions are defined as significant conditions or diseases that are present at signing of informed consent.

Medical history and concurrent medical conditions will be coded using the MedDRA coding system, and will be presented in the data listing. There will be no summary or inferential analysis of medical history and concurrent medical conditions.

## 7.6 Medication History and Concomitant Medications

Medication history information includes any medication stopped at or within 28 days prior to signing of informed consent. Medications used from signing of informed consent through the end of study will be considered as concomitant medications.

Medication history and concomitant medications will be coded using the WHO Drug, and will be presented in the data listing. There will be no summary or inferential analysis of medication history and concomitant medications.

## 7.7 Study Drug Exposure and Compliance

The date and time of each dose for each subject will be reported in the data listing for all subjects. Summaries and listings of TAK-906 PK data will be provided. No summary statistics for the extent of exposure to study drug or compliance calculations will be performed for this study.

## 7.8 Efficacy Analysis

Not applicable.

## 7.9 Pharmacokinetic/Pharmacodynamic Analysis

### 7.9.1 Pharmacokinetic Analysis

The schedule for blood and urine samples for PK analysis of TAK-906 and any measured metabolites is specified in [Appendix A](#).

[figure not shown]
The plasma of TAK-906 and any measured metabolites will be summarized by regimen (TAK-906 maleate alone and TAK-906 maleate with itraconazole) over each scheduled sampling time point using descriptive statistics (N, arithmetic mean, SD, CV%, median, minimum and maximum). Individual plasma and urine concentration data versus time will be presented together with the descriptive statistics as well as in separate data listings.

In addition, the figures for mean plasma concentrations of TAK-906 versus time (linear and semi-log scale) will be generated.

Plasma and urine PK parameters will be calculated from the plasma and urine concentration values versus time profile of TAK-906 and any measured metabolites using non-compartmental analysis. The key PK parameters are listed below:

#### *Plasma*

CCI

CCI  
[Redacted]

*Urine*

CCI  
[Redacted]

Additional plasma and/or urine PK parameters may be calculated if necessary, in accordance with the Clinical Pharmacology Analysis Plan (CPAP).

Plasma and urine PK parameters of TAK-906 and any measured metabolites will be summarized by regimen using descriptive statistics. In addition, geometric mean and %CV will be computed for  $C_{max}$  and AUCs ( $AUC_{last}$  and  $AUC_{\infty}$ ).

Box plots and scatter plots for  $C_{max}$  and AUCs ( $AUC_{last}$  and  $AUC_{\infty}$ ) will be generated by regimen.

For evaluation of potential effect of itraconazole on TAK-906 PK, paired t-tests and associated 90% confidence intervals (CIs) will be determined on the natural logarithms of  $C_{max}$  and AUCs ( $AUC_{last}$  and  $AUC_{\infty}$ ) to compare the exposure between regimens. The geometric mean of the relative bioavailability of the TAK-906 maleate with itraconazole regimen relative to the TAK-906 maleate alone regimen and the associated 90% CIs will be determined by exponentiating the appropriate estimates for the difference between regimens in the log-transformed parameters.

All PK parameters calculated will be presented in data listings.

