#### 9.3.1 PK Evaluations

[figure not shown]
The PK parameters of TAK-906 will be derived using noncompartmental analysis methods and will be determined from the concentration-time data for all evaluable subjects. Actual sampling times, rather than scheduled sampling times, will be used in all PK computations involving sampling times. A more detailed description will be given in the clinical pharmacology analysis plan.

The following plasma PK parameters for TAK-906 will be calculated on Day 1 of Trial Period 1 and Day 4 of Trial Period 2:

- $C_{\max}$
- $AUC_{\infty}$
- $t_{1/2}$

Other PK parameters may be calculated if deemed necessary for the interpretation of the data. All efforts will be made to obtain the PK samples at the exact nominal time relative to dosing. However, samples obtained within 10% of the nominal time from dosing will not be captured as a protocol deviation, as long as the exact time of the sample collection is noted on eCRF.

CCI

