**Figure 4.a Trial Schematic**

## 5.0 ANALYSIS ENDPOINTS

### 5.1 Primary Endpoints

The primary endpoints of the trial are the following plasma PK parameters for TAK-906 on Days 1 and 4:

- Maximum observed concentration ( $C_{max}$ ).
- Area under the concentration-time curve from time 0 to time of the last quantifiable concentration ( $AUC_{last}$ ).
- Area under the concentration-time curve from time 0 to infinity, calculated using the observed value of the last quantifiable concentration ( $AUC_{\infty}$ ).

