## 6.0 DETERMINATION OF SAMPLE SIZE

Approximately 12 subjects will be enrolled in this trial. The sample size justification is based on an acceptance range of 50% to 200% and assumes that the intrasubject %CV for  $AUC_{last}$  and  $C_{max}$  of TAK-906 will not exceed 25%. This sample size will provide 80% power to conclude plasma concentration of TAK-906 will not increase more than 2-fold in presence of itraconazole.

Subjects who drop out for nonsafety reasons may be replaced at the discretion of the investigator in consultation with the sponsor. Subjects who drop out for safety reasons will not be replaced.

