## 7.0 METHODS OF ANALYSIS AND PRESENTATION

### 7.1 General Principles

Continuous data will be summarized using descriptive statistics, including the number of subjects, mean, standard deviation (SD), median, minimum, and maximum. The coefficient of variation (%CV) and geometric mean will be included in the summary of continuous data where indicated. Categorical data will be summarized as the number and percentage of subjects in each category.

Arithmetic means, geometric means, and medians will be presented to 1 more decimal place than the recorded data, and SDs will be presented to 2 more decimal places than the recorded data, where appropriate. Where applicable, confidence intervals about a parameter estimate will be presented using the same number of decimal places as the parameter estimate and p-values will be rounded to 3 decimal places prior to assessment of statistical significance.

All study-related raw data for enrolled subjects, including derived data, will be presented in data listings. In addition, the actual day relative to the first dose will be presented, where applicable.

All statistical analyses will be performed using the SAS System Version 9.4.

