### 7.11.2 Clinical Laboratory Evaluations

Clinical safety laboratory tests include chemistry, hematology, urinalysis, and diagnostic screening. Refer to [Appendix A](#) for scheduled clinical laboratory test measurements and to [Appendix B](#) for the list of all clinical laboratory tests.

Descriptive statistics (N, mean, median, SD, minimum and maximum) of clinical safety laboratory variables will be summarized for baseline, post-dosing, and change from baseline at each visit. Only the scheduled measurements will be included in the summary. No inferential analysis will be performed.

Individual results for hematology and chemistry laboratory tests will be evaluated against the Takeda predefined laboratory markedly abnormal value (MAV) criteria ([Appendix C](#)). All subjects that meet the MAV criteria will be presented in a data listing. If a subject has a MAV for a particular laboratory test, all visits for that subject for that parameter will be listed. The number and percentage of subjects with at least 1 post dose markedly abnormal laboratory test result will be summarized by regimen. The mapping of the subjects with post dose results which meet the MAV criteria will be listed as a table. All post dose clinical lab results within 7 days of the last

dose, including scheduled and unscheduled measurements will be included in the MAV summaries.

All clinical laboratory data will be presented in both SI and conventional units in the data listings. Laboratory data outside of the normal reference range will be flagged on the listing along with values meeting MAV criteria.

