### 7.11.3 Vital Signs

Vital sign measurements include body temperature, pulse, respiratory rate, and blood pressure. Refer to [Appendix A](#) for scheduled vital signs measurement visits.

Descriptive statistics (N, mean, median, SD, minimum and maximum) of these vital signs will be summarized by regimen for baseline, post-dosing, and change from baseline at each scheduled time point. For each regimen (period), baseline is defined as the last non-missing vital sign measurement at or prior to predose (time relative to TAK-906 dosing) in the corresponding period. Only the vital signs collected at the scheduled visits or time points will be included in the summary. No inferential analysis will be performed for the observed vital signs.

All individual vital signs that meet Takeda's predefined criteria for markedly abnormal values ([Appendix D](#)) will be listed. The number and percentage of subjects with at least 1 post dose markedly abnormal vital sign measurement will be summarized by regimen. The mapping of the subjects with post dose results which meet the MAV criteria will be listed as a table. All post dose vital signs within 7 days of the last dose, including both scheduled and unscheduled measurements, will be included in the MAV summaries.

All vital sign data will be presented in the listings. Vital sign MAVs will be flagged in the listings.

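### Does SAP 7.9.1 need an explicit rule tying its 90% confidence intervals to the 2-fold limit on which the trial is sized?

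*SAP*

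**What the plan says.** Section 6.0 of the SAP, like Protocol 11.3, plans about 12 subjects, uses an acceptance range of 50% to 200%, and assumes an intrasubject CV of at most 25% for AUClast and Cmax. It states the aim as follows: "This sample size will provide 80% power to conclude plasma concentration of TAK-906 will not increase more than 2-fold in presence of itraconazole".

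The analysis is in SAP 7.9.1: "paired t-tests and associated 90% confidence intervals (CIs) will be determined on the natural logarithms of" Cmax, AUClast and AUCinf, to compare exposure between the two regimens. The log differences are then exponentiated to give the ratio of TAK-906 with itraconazole to TAK-906 alone, with its 90% CI. No null value, level or limit is stated there. Protocol 11.1.3 has almost the same text and leaves the detail to the SAP.

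Two other places bear on the point.

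- SAP 7.1, in a sentence on decimal places that begins with the words where applicable, says that "p-values will be rounded to 3 decimal places prior to assessment of statistical significance".
- SAP 5.1 introduces three parameters (Cmax, AUClast, AUCinf) with "The primary endpoints of the trial are the following plasma PK parameters for TAK-906 on Days 1 and 4". The list in Protocol 9.3.1, introduced by "The following plasma PK parameters for TAK-906 will be calculated on Day 1 of Trial Period 1 and Day 4 of Trial Period 2", prints Cmax, AUCinf and t1/2.

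**The concern.** The sizing section and the analysis section seem to ask different questions. Section 6.0 asks whether exposure stays below twice its value without the inhibitor. A paired t-test on log values, with no other null stated, tests whether the ratio equals 1. A trial can reject a ratio of 1 and still show clearly that the increase is below 2-fold, or the reverse.

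SAP 7.1 mentions assessing significance but gives no level. A 90% CI suggests 0.10, and common habit suggests 0.05. The SAP rules out inference elsewhere: "There will be no inferential analysis of demographic and baseline characteristics" in 7.4, "No inferential analysis will be performed" for laboratory tests, "No inferential analysis will be performed for the observed vital signs" in 7.11.3, and likewise for ECGs in 7.11.4. That leaves the paired t-tests as the only named test to which the rounding sentence could apply.

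Nor does the plan say which parameters must meet the 2-fold limit. Section 6.0 names AUClast and Cmax, but only for the CV. The conclusion itself refers to plasma concentration, and the primary endpoints add AUCinf. If Cmax and AUC rise by different amounts, the 2-fold statement could hold for one and fail for the other, and the report could choose between them after the fact.

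**Working it through.** **Inputs from the documents.** n = 12, each subject as own control; intrasubject CV at most 25%; limits 0.50 and 2.00; 90% CI; stated power 80% (SAP 6.0 and 7.9.1).

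**Assumptions.** The documents give no true ratio, so a range is shown. The 90% CI corresponds to a one-sided level of 0.05 at each limit. The t-test is taken against ratio 1 at two-sided 0.05 and 0.10.

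**Standard error.** Within-subject log SD = sqrt(ln(1 + 0.25²)) = 0.2462. SE of the mean paired log difference = 0.2462 × sqrt(2/12) = 0.1005, with 11 df. At CV 20% and 15% the SE is 0.0809 and 0.0609.

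**Width of the interval.** t(0.95, 11) = 1.796, and exp(1.796 × 0.1005) = 1.198. At CV 25% the 90% CI therefore runs from about the estimate divided by 1.20 to the estimate times 1.20.

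**The plan's own 80%.** The probability that the upper 90% limit is below 2.00 is P(T < −1.796), where T is noncentral t with 11 df and ncp = (ln r − ln 2)/SE. It equals 0.80 at a true ratio r of 1.53: (0.4263 − 0.6931)/0.1005 = −2.65. At one-sided 0.025 the ratio is 1.47. At r = 1.00 power exceeds 99.9%. Because the plan does not state the true ratio, the 80% can be neither confirmed nor refuted, but the CI-against-2.00 reading gives it at a plausible value.

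**Limit against t-test, CV 25%.** For the t-test, ncp = ln r/SE.

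| True ratio | 90% CI below 2.00 | p<0.05 for ratio 1 | p<0.10 for ratio 1 |
|---|---|---|---|
| 1.10 | >99.9% | 14.0% | 23.1% |
| 1.25 | 99.7% | 52.6% | 66.9% |
| 1.50 | 85.0% | 95.6% | 98.3% |
| 1.60 | 66.8% | 98.9% | 99.7% |

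So the two questions do separate. At r = 1.50 the CI lies within the limits and p<0.05 in about 81% of trials: a real increase that is still below 2-fold. These are compatible findings, and the ratio with its CI shows both.

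**Upper limit or whole interval.** At r = 1.25, 1.5 and 1.8 the whole CI lies within 0.50 to 2.00 with probability 0.997, 0.849 and 0.253; the upper limit alone gives 0.997, 0.850 and 0.254. The readings agree for increases, which is what Section 6.0's conclusion concerns. They part only for a marked decrease, where the whole-CI reading is met in 79% (r = 0.65) and 52% (r = 0.60).

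**Which parameter.** Simulation of two parameters, 200,000 trials per case, correlation of log differences 0.5 to 0.95, CV 25%:

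| True Cmax / AUC ratios | One below 2.00 is enough | Both must be below 2.00 |
|---|---|---|
| 1.53 / 1.53 | 83.8 to 91.5% | 68.2 to 76.4% |
| 1.3 / 1.6 | about 99% | about 67% |
| 1.5 / 2.0 | about 85% | about 5% |

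In the 1.3/1.6 case the both-must-pass figure rises to about 83% at CV 20% and 96% at CV 15%. These rows evaluate combined pass rules, which neither document proposes.

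**AUClast in Protocol 9.3.1.** AUClast is a primary endpoint in Protocol 5.2.1 and SAP 5.1 and is analysed by name in SAP 7.9.1. Section 9.3.1 allows other parameters to be calculated, and part of that section is redacted. The shorter list does not put the calculation of AUClast in doubt.

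**The case for a change.** The best case for a change is that a plan should state its decision rule before an open-label trial reads out. The protocol defers detail to the SAP, yet the SAP nearly repeats the protocol's sentence. The inferential paragraph is printed whole, so redaction does not explain the gap, and the Clinical Pharmacology Analysis Plan is cited only for additional PK parameters. Two sentences would settle the limit, the parameters and the role of the p-values.

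The factual part stands: Section 7.9.1 does not refer to the 2-fold limit, and no level is given. The rest is weaker.

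- A ratio of 1 is the natural default null, but it is inferred. The SAP does not state it.
- SAP 7.1 is a general rounding convention that applies where relevant. It does not plan a significance decision on exposure.
- Section 7.9.1 does name the three parameters for the tests and intervals. What is unwritten is only the link from the limit to those parameters.
- The primary objective is to evaluate the effect of itraconazole on TAK-906 PK, which is estimation. The visible text hangs no success criterion or action on a combined pass across parameters. If Cmax and AUC diverge, the planned output shows this, because each has its own ratio and CI.

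**Conclusion.** The concern does not call for a change. It identifies a cross-reference that the SAP leaves unwritten but supplies in substance: Section 6.0 gives an acceptance range for a ratio, and Section 7.9.1 gives the 90% CI of that ratio. Reading one against the other is standard practice and is compatible with the stated power, which it yields at a true ratio of 1.53.

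The t-test of ratio 1 would indeed mislead if it were used for the 2-fold question (53% against 99.7% at a true ratio of 1.25), but nothing in the plan uses it so. For assumed true ratios of about 0.80 to 1.25 at CV 25%, the limit is met on a single parameter in over 99% of trials under either the upper-limit or the whole-interval reading. At larger ratios the answer may differ by parameter, and the planned tables will show which. An explicit rule would leave the parameters for the sponsor to name and would alter no estimate, interval or sample size.

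This rests on the ratios and intervals being reported for all three primary parameters, as Section 7.9.1 provides. The shorter list in Protocol 9.3.1 is at most a clerical slip without consequence.

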### 7.9.2 Pharmacodynamic Analysis

Not applicable.

### 7.10 Other Outcomes

Not applicable.

### 7.11 Safety Analysis

Safety analyses include adverse events (AEs), clinical laboratory parameters, vital sign parameters, 12-lead electrocardiogram (ECG) results, and physical examination.

All summaries of safety data are based on subjects in the Safety Analysis Set.

#### 7.11.1 Adverse Events

A treatment-emergent adverse event (TEAE) will be defined as an AE or serious adverse event (SAE) that started or worsened after first study drug administration and within 30 days of last dose of study drug (onset date – date of last dose + 1  $\leq$  30). All AE verbatim terms will be coded by system organ class (SOC) and preferred term (PT) using the MedDRA dictionary.

TEAEs will be summarized by overall and the following categories: Period 1 (onset on and after TAK-906 dosing on Period 1 Day 1 and before the dosing of itraconazole on Period 2 Day 1), Period 2 Day 1 post-dose to Day 4 pre-dose (after itraconazole dosing on Period 2 Day 1 and before TAK-906 dosing on Period 2 Day 4), and Period 2 Day 4 post-dose and thereafter (after TAK-906 and itraconazole dosing on Period 2 Day 4). The tables will include the number and percentage (N [%]) of subjects reporting any event for that term. The following is a list of TEAE summary tables to be generated.

- Overview of TEAEs (at both subject and event level).
- TEAEs by SOC and PT (at both subject and event level).
- Subject Mappings for TEAEs.
- TEAEs by PT.
- Relationship of TEAEs to Study Drug by SOC and PT.
- Drug-Related TEAEs by SOC and PT.
- Intensity of TEAEs by SOC and PT.
- Intensity of Drug-Related TEAEs by SOC and PT.

For each category and overall, subjects reporting more than 1 occurrence for a term (SOC or PT) being summarized will be counted only once using the most extreme incident (most severe for the intensity tables and related for the relationship to study drug tables).

Data listings will be provided for all TEAEs, PTEs, TEAEs that led to study drug discontinuation, TEAEs that led to abnormal liver functions, SAEs, AEs that resulted in death, and AEs occurring more than 30 days after the last dose of study medication.

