Number of Subjects: 12	Number of Sites: 1 site
Dose Levels: TAK-906 maleate 25 mg QD Itraconazole 200 mg QD	Route of Administration: TAK-906 maleate: PO Itraconazole: PO
Duration of Treatment: 2 QD TAK-906 maleate doses 5 QD itraconazole doses	Period of Evaluation: Approximately 7 to 8 weeks

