## **6.0 TRIAL DESIGN AND DESCRIPTION**

### **6.1 Trial Design**

This is a phase 1, single-sequence, open-label, 2-period crossover trial in approximately 12 healthy male and female (nonchildbearing-potential) subjects. The trial is designed to investigate the effect of a potent CYP3A4 inhibitor (itraconazole) on the PK of TAK-906.

The trial will include a Screening Visit, a Period 1 (Days 1 to 3), followed by a minimum of a 4-day washout from the time of TAK-906 maleate dose, a Period 2 (Days 1 to 6), and a Follow-up Visit.

On Day 1 of Period 1, eligible subjects will be enrolled into the trial and will receive a single PO dose of TAK-906 maleate 25 mg. On Days 1 to 5, inclusive, of Period 2, subjects will receive itraconazole 200 mg once daily (QD) PO solution. Following after an overnight fast of at least 8 hours, a single PO dose of TAK-906 maleate 25 mg will be administered 1 hour after the itraconazole dose on Day 4 of Period 2. Both doses of TAK-906 maleate will be administered after an overnight fast of at least 8 hours as food reduces its bioavailability by approximately 40%.

Itraconazole will be administered to subjects under clinic supervision on an outpatient basis on the morning of Days 1 to 3 of Period 2 and during confinement on Days 4 to 5 of Period 2.

Blood samples for assessment of TAK-906 concentrations will be collected from predose to 48 hours after each dose of TAK-906 maleate. Samples may be assayed for TAK-906 metabolites if deemed necessary. Urine samples will be collected through 48 hours and may be assayed for TAK-906 concentrations and metabolites if deemed necessary for the interpretation of data.

Whole blood samples for deoxyribonucleic acid (DNA) pharmacogenomics (PGx) analysis and ribonucleic acid (RNA) isolation will be collected predose on Day 1 of Trial Period 1.

Safety will be assessed by monitoring for adverse events, vital signs, ECGs, clinical laboratory results, and physical examinations throughout each dosing period.

After completion of the trial (or following subject withdrawal), all subjects will return for a Follow-up Visit 10 to 14 days after their last dose of TAK-906 maleate.

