## **10.2.9 Collection and Reporting of AEs, SAEs, Special Interest AEs, and Abnormal LFTs**

### *10.2.9.1 Collection Period*

Collection of AEs (ie, AEs, SAEs, special interest AEs, and abnormal LFTs) will commence at the time the subject signs the informed consent. Routine collection of AEs will continue until the Follow-up Visit 10 to 14 days after the last dose of TAK-906. For subjects who discontinue prior to the administration of trial medication, AEs will be followed until the subject discontinues trial participation.

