#### **11.1.4 Safety Analysis**

The safety set will be used for all summaries of safety parameters. These summaries will be presented by regimen (TAK-906 maleate alone, itraconazole alone, and TAK-906 maleate with itraconazole).

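### The TAK-906-alone and combination adverse event columns cover windows whose relative length depends on scheduling, so their crude percentages can differ for that reason alone

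*SAP*

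**What the plan says.** SAP 7.11.1 divides TEAEs into three consecutive onset categories, plus an overall column.

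- TAK-906 alone: "Period 1 (onset on and after TAK-906 dosing on Period 1 Day 1 and before the dosing of itraconazole on Period 2 Day 1".
- Itraconazole alone: from that itraconazole dose to the TAK-906 dose on Period 2 Day 4, about 3 days.
- Combination: "Period 2 Day 4 post-dose and thereafter (after TAK-906 and itraconazole dosing on Period 2 Day 4". No end is given beyond the general TEAE limit, "within 30 days of last dose of study drug".

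The SAP labels the categories by period and day. They carry out the instruction in Protocol 11.1.4: "These summaries will be presented by regimen (TAK-906 maleate alone, itraconazole alone, and TAK-906 maleate with itraconazole".

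The statistic is a crude count: "The tables will include the number and percentage (N [%]) of subjects reporting any event for that term". Two of the tables also count events. SAP 7.7 plans no summary of exposure.

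Two protocol rules set the lengths. Period 1 is "followed by a minimum of a 4-day washout from the time of TAK-906 maleate dose" (Protocol 6.1), and no maximum washout is stated. At the other end, "Routine collection of AEs will continue until the Follow-up Visit 10 to 14 days after the last dose of TAK-906" (Protocol 10.2.9.1). The trial summary puts the period of evaluation at "Approximately 7 to 8 weeks".

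**The concern.** The only secondary objective is the safety and tolerability of one TAK-906 dose with and without the inhibitor. For adverse events, the main display of that contrast is the first column against the third. A subject observed for longer has more chance to report an event, whatever was taken. If the columns cover different numbers of days, part of any difference in percentages reflects the calendar. With 12 subjects, one subject is 8.3 percentage points, so a small artefact is visible. The tables do not show how many days stand behind each column, so a reader cannot allow for it.

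**Working it through.** The documents state no window length or ratio, so there is no planned figure to reproduce.

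**Inputs.** W = days from the Period 1 TAK-906 dose to the first itraconazole dose (at least 4; Protocol 6.1). F = days from the Period 2 Day 4 TAK-906 dose to the Follow-up Visit (10 to 14; Protocol 10.2.9.1). Screening starts on Day -28, and Period 2 Day 1 to Day 4 is 3 days (Protocol 3.0).

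**Lengths.** Ratio = F/W. Total = 28 + W + 3 + F, assuming full screening and that the period of evaluation includes it.

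| W | F | Ratio F/W | Total days | Weeks |
|---|---|---|---|---|
| 4 | 10 | 2.50 | 45 | 6.4 |
| 4 | 14 | 3.50 | 49 | 7.0 |
| 8 | 10 | 1.25 | 49 | 7.0 |
| 9.5 | 12 | 1.26 | 52.5 | 7.5 |
| 11 | 14 | 1.27 | 56 | 8.0 |
| 15 | 10 | 0.67 | 56 | 8.0 |

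The ratio is 1 when W = F. Even at a fixed 52.5 days it runs from 10/11.5 = 0.87 to 14/7.5 = 1.87, depending on how the days are split. Shorter screening leaves room for a longer washout and a lower ratio.

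**Effect on counts.** Every event rate here is an assumption. Take no drug effect, 12 subjects in both periods and a flat daily rate r. The proportion with an event in d days is 1 - exp(-r*d), and the shift toward the combination is 12 * [exp(-r*W) - exp(-r*F)].

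At r = 0.02:

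- W = 4: 7.7% in 4 days, against 18.1% in 10 and 24.4% in 14. Shift 1.25 to 2.01 subjects.
- W = 9.5, F = 12: 17.3% against 21.3%. Shift 0.48.
- W = 15, F = 10: 25.9% against 18.1%. Shift 0.93 toward TAK-906 alone.

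Other flat rates:

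| r per day | W = 4, F = 10 to 14, toward combination | W = 15, F = 10, toward TAK-906 alone |
|---|---|---|
| 0.005 | 0.35 to 0.57 | 0.28 |
| 0.05 | 2.55 to 3.87 | 1.61 |

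**Front-loaded events.** A flat rate may overstate late events, since subjects leave the unit at 48 hours. Let the rate after 48 hours be k times the early rate, so the cumulative hazard is r*(2 + k*(d - 2)). At r = 0.02, W = 4, F = 10 to 14:

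- k = 0.5: 5.8% against 11.3% to 14.8%. Shift 0.66 to 1.08.
- k = 0.25: 4.9% against 7.7% to 9.5%. Shift 0.34 to 0.56.
- k = 0: 3.9% in both. Shift 0.

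Equal windows give a shift of 0 at every r and k.

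**The case against.** The case for leaving the plan alone is substantial.

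- The tables are descriptive; no test or decision hangs on them, and the category boundaries are stated openly.
- Confinement runs to 48 hours after TAK-906 in both periods (Protocol 9.5), so the closest observation is already matched.
- Relationship and intensity tables, subject mappings and listings are planned. With about 12 subjects, a reader can inspect every onset.
- Vital signs and ECGs serve the same objective, with period-specific baselines and post-dose times aligned to TAK-906 (SAP 7.11.3 and 7.11.4).
- Matching the windows would not isolate the interaction in a single-sequence, open-label design.

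All of this stands, and it limits the weight of the point. It does not remove it. Relatedness is judged with the treatment known, and listings leave the reader to rebuild the contrast by hand.

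Three stronger readings are tempting, and the documents do not support them.

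- *The combination column is generally 2.5 to 3.5 times as long and so biased against the combination.* That ratio belongs to the minimum washout. With full screening, the 4-day/10-day schedule totals 6.4 weeks, short of the stated period, and the 4-day/14-day schedule only just reaches 7.0. Longer washouts bring the ratio to 1 or reverse it.
- *The 30-day limit makes the ratio 30/4 = 7.5.* That limit says which onsets count as TEAEs. Routine collection stops at Follow-up.
- *After Follow-up, only spontaneously reported related SAEs can enter, so the 30-day rule needs a corrective footnote.* Protocol 10.2.9.2 has subjects with adverse events monitored until these resolve or are explained, Protocol 10.1 can record a worsening as a new event, and the TEAE definition includes worsening. Such a footnote would be inaccurate.

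**Conclusion.** The point holds as a schedule-dependent weakness in one descriptive display. The two columns that carry the TAK-906 contrast have no fixed relative length, and no planned adverse event table puts the two doses on an equal post-dose window.

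Neither direction nor size can be fixed from the documents, which give no maximum washout, event rate or event timing. At a 4-day washout, the shift is nil if all events fall within 48 hours and 1.3 to 2.0 of 12 subjects at an assumed flat 2% per day. The largest value calculated, 3.87, needs a flat 5% per day with 14-day follow-up: about half of healthy subjects (50.3%) reporting an event in 14 days without any drug effect. That is an upper illustration, not an expectation.

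The primary pharmacokinetic analysis is untouched. This is a cheap improvement worth making, not a threat to the trial's main conclusion.

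**What to change.** In SAP 7.11.1, keep the three categories, the overall column and all listings, and make two additions.

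1. One descriptive table of TEAEs with onset from each TAK-906 dose to 96 hours after it (the stated minimum washout), TAK-906 alone beside TAK-906 with itraconazole. For any subject whose first itraconazole dose comes less than 96 hours after the Period 1 TAK-906 dose, cut both windows at the same elapsed time. The protocol counts washout from the time of dosing, so this should be rare. If the site counts calendar days, a 0900 dose followed by a 0600 dose (Protocol 9.4 allows 0600 to 0900) gives 96 - 3 = 93 hours.
2. The median and range of observed days under each existing category heading.

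Leave later-onset TEAEs in the existing tables and listings. Separate late-onset columns by regimen would recreate the problem: at a 4-day washout they would cover 0 days against 6 to 10.

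The cost is SAP wording, one table and a line under the headings. Event start times (Protocol 10.2.9.2) and dose times (SAP 7.7) are already recorded. No new data are needed and no event is dropped from reporting.

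The downside is that late events leave this one contrast. At the stated half-life of about 4 hours, 96 hours is 96/4 = 24 half-lives. If inhibition lengthened it fivefold (an assumption), it is 96/20 = 4.8 half-lives, with 2^-4.8 = 3.6% remaining. Period effects and itraconazole's own effects, including the Day 5 dose inside the 96 hours, also remain, and a footnote to the table should say so.
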